5.2 EXCLUSION CRITERIA

Any of the following will exclude potential subjects from the study:

1. Clinically significant acute or chronic liver disease of an etiology other than PSC.

- a. Patients with stable treated overlapping PSC and autoimmune hepatitis (AIH) will be allowed to enroll into the study.
 - i. Stable treated overlapping PSC/AIH is defined as on a consistent regimen of immunosuppressive therapy for a minimum of 12 weeks and no evidence of a hepatic flare during that time period.
2. Secondary or IgG4-related sclerosing cholangitis
3. Presence of a dominant stricture of **clinical** concern on MRCP at Screening.
 - a. Patients with dominant stricture can be enrolled if the investigator feels there is no evidence on magnetic resonance imaging or cholangiography indicative of cholangiocarcinoma or that the stricture will not result in significant fluctuations in ALP during Screening or Study period.
 - b. Patients with a dominant stricture must have a total bilirubin of ≤ 2.5 mg/dL for at least 6 months prior to Screening.
4. Placement of a bile-duct stent or percutaneous bile-duct drain within 3 months of Screening
 - a. Patients who have undergone a balloon dilation procedure of a stricture will be allowed to enroll into the study after a minimum of 4 weeks post-procedure.
5. History, evidence, or high suspicion of cholangiocarcinoma or other hepatobiliary malignancy based on imaging, screening laboratory values, and/or clinical symptoms
6. Acute cholangitis within 12 weeks of Screening and through Day 1
 - a. Chronic preventive antibiotics for cholangitis will be allowed in the study.
 - b. Intermittent courses of antibiotics for the presumptive treatment of cholangitis are allowed if outside the 12-week window prior to Screening.
7. Evidence of decompensated cirrhosis (Child-Pugh B or C) based on histology, relevant medical complications, or laboratory parameters.
 - a. Patients with compensated cirrhosis will be allowed to enroll into the study.
 - b. Patients with pre-sinusoidal esophageal varices with no history or evidence of bleeding may be enrolled as long as there is no other evidence of hepatic decompensation.
8. Prior liver transplantation
9. Any contraindication or inability to obtain a screening MRCP or colonoscopy (only in patients with concomitant IBD, if historical colonoscopy within the 12-month window is not available)

10. Screening electrocardiogram (ECG) with clinically significant abnormalities as determined by the Investigator
11. Positive for HBsAg, HCV-RNA, or anti-HIV
12. History of malignancy diagnosed or treated within 2 years (recent localized treatment of squamous or non-invasive basal cell skin cancers is permitted; cervical carcinoma in situ is allowed if appropriately treated prior to Screening); subjects under evaluation for malignancy are not eligible.
13. Clinically-relevant drug or alcohol abuse within 12 months of screening. A positive drug screen will exclude subjects unless it can be explained by a prescribed medication.
14. Use of any prohibited concomitant medications as described in [Section 5.7](#) within 4 weeks of Day 1 visit
15. Patients with severe allergic or anaphylactic reactions to recombinant therapeutic proteins, fusion proteins, or chimeric, human, or humanized antibodies
16. Participation in a study of another investigational agent within 4 weeks or five half-lives of the investigational drug (whichever is longer) prior to Screening
17. History of clinically significant unstable or untreated illness or any other major medical disorder that may interfere with subject treatment, assessment, or compliance with the protocol
18. Any acute or chronic condition or other disease that, in the opinion of the Investigator, would limit the patient's ability to complete and/or participate in this clinical study
19. Presence of any other conditions (e.g., geographic or social), actual or projected, that the investigator feels would restrict or limit the patient's participation for the duration of the study
20. Employment by NGM, participating contract research organization (CRO), or study site (permanent, temporary contract worker, or designee responsible for the conduct of the study) or are immediate family of an NGM employee, participating CRO, or study-site employee (hence, conflict of interest issues). Immediate family is defined as a spouse, parent, child, or sibling, whether biological or legally adopted.

The Investigator has discretion to repeat assessments/procedures if he/she believes there is a good chance the results were spurious and do not accurately represent the subject's true values. Repeat assessments/procedures must be conducted within the 6-week Screening Period, prior to randomization, and a subject may only be rescreened for these labs a single time.

5.3 DISCONTINUATION OF STUDY TREATMENT IN AN INDIVIDUAL SUBJECT

Study treatment will be discontinued if any of the following CTCAE categories or abnormal elevations in liver function tests occurs on-treatment:

- Any Grade 3 TEAE related to study drug
- Any Grade 4 or higher TEAE
- Elevation of ALT **and** total bilirubin > 2 times above subject-specific baseline value calculated using the median of the Screening and Day 1 value
 - ALT, AST, and total bilirubin must be re-tested within 72 hours.
 - Subjects with persistent elevations should be discontinued from treatment, independent of whether or not they are symptomatic.
- Elevation of ALT > 2 times above subject-specific baseline
 - ALT, AST, and total bilirubin must be re-tested within 72 hours.
 - Subjects with persistent elevations who are asymptomatic may continue treatment under protocol-defined *close observation* criteria.
 - Subjects with persistent elevations who are symptomatic must discontinue treatment.
 - Subjects continuing treatment under *close observation* should implement study procedures and assessments as part of the study conduct:
 1. Repeat liver enzyme and serum bilirubin tests two or three times weekly. The frequency of retesting can decrease to once a week or less if abnormalities stabilize or the trial drug has been discontinued and the subject is asymptomatic.
 2. Repeat additional tests to evaluate liver synthetic function (e.g., INR, direct bilirubin) as appropriate.
 3. Obtain a detailed history of symptoms and prior or concurrent diseases.
 4. Obtain a history of concomitant drug use (including nonprescription medications and herbal and dietary supplement preparations), alcohol use, recreational drug use, environmental toxin exposure, and special diets.
 5. Rule out acute viral hepatitis and other acute or chronic hepatobiliary diseases.

Dose reductions or increases are not allowed as part the study conduct.

5.4 DISCONTINUATION OF SUBJECTS FROM STUDY PARTICIPATION

Patients will be informed that they are free to withdraw from the study at any time and for any reason. The Principal Investigator (PI) may remove a subject from the study if, in the PI's opinion, it is not in the best interest of the subject to continue the study. Subjects may be discontinued due to subject's personal withdrawal of consent, due to subject's

non-compliance of the study-drug prescription, due to a change in compliance with an inclusion/exclusion criterion that is clinically relevant and affects subject safety, due to a site/subject's protocol deviation, due to subject being considered lost-to-follow-up, due to any code-breaking requested by investigator/safety, due to NGM opting to terminate study, due to a subject experiencing an AE(s), due to a subject experiencing a pregnancy, or due to an administration of non-permitted concomitant medication that might affect subject safety or study assessments/objectives. Notification of discontinuation will be made immediately to the Sponsor's Medical Monitor. In case of premature discontinuation of study participation, efforts will be made to perform all final Week 12 (EOT) and Week 16 (EOS) visits/assessments. The date the subject is withdrawn from the study and the reason for discontinuation will be recorded on the subject's electronic Case Report Form (eCRF). All withdrawn subjects will be followed until resolution of any AEs or until any unresolved AEs are judged by the PI to have stabilized.

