6.5 REMOVAL OF STUDY BLIND

This will be a double-blind, placebo-controlled study. Breaking of the blind will be available to the PI through an [REDACTED]. The subject's treatment assignment will be available to the PI in the event of a medical emergency or an AE that necessitated identification of the study drug for the welfare of that subject. Except in the case of a medical emergency, the PI and clinic staff will remain blinded during the conduct of the study and until such time that all discrepancies in the clinical database are resolved (i.e., at the time of the database lock). The date and time when the PI removed the study blind for an individual subject will be documented by the [REDACTED] and an automated notification will be sent to the Sponsor. The contracted CRO's pharmacovigilance team may also be required to break the blind for regulatory reporting purposes.

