8.4.3 Full Analysis Set

All randomized subjects who receive at least one dose (full or partial) of study drug and have at least one valid, non-missing post-dose efficacy/PD parameter value will be included in the Full Analysis Set (FAS). This will be the set for the primary analyses of efficacy and PD endpoints. In FAS analyses, subjects will be grouped according to randomized treatment if this differs from actual treatment received.

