8.4.4 Per Protocol Set

The Per Protocol Set (PPS) will constitute a subset of the FAS. It will include subjects who have at least one valid, non-missing post-dose ALP measurement. In addition, FAS subjects who deviate from the conduct of the study or have an AE deemed by the Medical Monitor to be impactful on the primary endpoint will be excluded from the PPS. In associated analyses, subjects will be grouped according to actual treatment received, if it differs from the randomized treatment.

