4.1. Disposition

Subject disposition will be summarized for the randomized Set. A summary of the analysis sets includes the number and percentage of subjects for the following categories: subjects randomized, subjects who completed treatment, subjects who completed the study, subjects who discontinued

from the study, subjects in Safety Set, subjects in the FAS Set, subjects in the PP Set, and subjects in the pharmacokinetic Set. All percentages will be based on the number of subjects randomized.

Primary reason for treatment discontinuation and primary reason for study discontinuation will be summarized in the disposition table. Reasons for study discontinuation include the following: adverse event, death, lost to follow-up, trial screen failure, withdrawal of consent by subject, subject refused to return for follow-up visit, other.

A listing to subject disposition data will be presented for each subject, including enrollment date, treatment start date, treatment end date, treatment discontinuation reason and study discontinuation reason.

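### Protocol 5.4 allows subjects to be taken off study, not just off drug, for four non-safety reasons, so the Week 12 ALP of some deviators may be missing from the FAS analysis

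*Protocol*

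**What the plan says.** Protocol 5.3 deals with stopping study treatment. Section 5.4 deals with leaving the study, and its wording is permissive: "Subjects may be discontinued due to subject's personal withdrawal of consent" opens a list of reasons. The list includes non-compliance with study drug, then "due to a site/subject's protocol deviation, due to subject being considered lost-to-follow-up, due to any code-breaking requested by investigator/safety", and later "due to an administration of non-permitted concomitant medication that might affect subject safety or study assessments/objectives". The deviation ground has no threshold, whereas the eligibility-change ground in the same sentence is confined to changes that matter clinically and bear on safety.

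The same paragraph undertakes to try to carry out the final Week 12 and Week 16 visits for anyone who leaves early. Protocol 5.6.7 runs Week 12 and Early Withdrawal as one visit, with early leavers then booked for a follow-up four weeks later. Section 5.6.8 places the Week 16 visit four weeks after the last dose.

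The primary analysis uses the FAS: "In FAS analyses, subjects will be grouped according to randomized treatment if this differs from actual treatment received" (Protocol 8.4.3). The PPS sensitivity analysis leaves out "FAS subjects who deviate from the conduct of the study", as well as subjects with an AE judged to affect the primary endpoint (Protocol 8.4.4). SAP Section 3 sets the Week 12 analysis window at Days 81 to 87.

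SAP 4.1 gives the reasons for study discontinuation as "adverse event, death, lost to follow-up, trial screen failure, withdrawal of consent by subject, subject refused to return for follow-up visit, other".

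**The concern.** All four grounds arise after randomization, and each may depend on treatment or on how ALP is moving. None requires the subject to stop giving blood samples. A FAS analysis by randomized treatment is most informative when such subjects are still measured at Week 12. The PPS analysis then shows what changes when they are left out.

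The grounds for leaving the study overlap with the grounds for exclusion from the PPS. To the extent that 5.4 is used, the subjects who distinguish the two sets are the ones whose Week 12 ALP is at risk in the FAS too. The FAS result would then lean on a missing-at-random model or on carried-forward values for them. With 20 randomized per arm, each lost subject is 5% of an arm.

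**Working it through.** **Inputs.** Protocol 8.1 (repeated in SAP 3.1) gives a mean ALP change on NGM282 of −75 with UDCA and −475 without, 0 on placebo, equal cells, SD 200, 20 randomized per arm, 20% dropout, and two-sided alpha of 0.027 per comparison. The visit windows come from SAP Section 3, and the visit rules from Protocol 5.4, 5.6.7 and 5.6.8.

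**1. The plan's own figure.** The mean difference is (75 + 475)/2 = 275. Completers are 20 × (1 − 0.20) = 16 per arm. The standard error is 200 × √(2/16) = 70.7, and 275/70.7 = 3.89. Power is 95.3% by the normal approximation, 94.1% by non-central t with 3 × 16 − 7 = 41 df, and 93.5% with 30 df. The stated power of at least 90% is reproduced.

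**2. When an early leaver's last ALP is taken.** The follow-up is booked four weeks after the Early Withdrawal visit (5.6.7), and the end-of-study visit falls four weeks after the last dose (5.6.8). Together these put the Early Withdrawal visit near the last dose, not at Day 84. This is the natural reading, but the documents do not say so outright.

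**3. Where that ALP lands.** The SAP windows are Days 4–10, 11–17, 25–31, 53–59 and 81–87. From Day 4 to Day 80 there are 77 days:

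- 4 × 7 = 28 days belong to an earlier visit.
- Days 18–24, 32–52 and 60–80, that is 7 + 21 + 21 = 49 days, belong to no visit.
- None belongs to Week 12.

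**4. Most that retention could add in power.** If every assumed dropout kept a Week 12 ALP (20 instead of 16 per arm, same mean and SD as completers), power would rise from 94.1% to 97.9%, or about 4 points. This is an upper bound, because the four grounds account for only an unknown part of the 20%.

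**5. Illustration of bias.** Assume that a fraction f of each arm is removed, that all of them lose their Week 12 ALP, that removed active subjects would have had no drug effect at Week 12, and that the analysis still returns the completers' effect of 275. The as-randomized effect is then 275 × (1 − f).

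- f = 0.10 (2 of 20): 247.5; 275/247.5 = 1.11, an 11% overstatement.
- f = 0.20 (4 of 20, the whole dropout allowance): 220; 275/220 = 1.25, a 25% overstatement.
- f = 0.10, and the removed placebo subjects had also started a drug lowering ALP by 150: the placebo mean is 0.10 × (−150) = −15, so the effect is 247.5 − 15 = 232.5; 275/232.5 = 1.18, an 18% overstatement.
- If removed subjects would have shown the same effect as completers, and placebo subjects started no such drug, the overstatement is zero.

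The documents support no particular f and no particular effect in those removed.

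**The case against.** The case against is substantial, and it removes any claim of certain loss.

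- Removal is optional. Elsewhere the protocol expects deviators to stay: 5.5 brings out-of-window subjects back onto schedule, and 5.7 sends medication changes to the Medical Monitor without automatic removal.
- Section 5.4 itself provides for Week 12 and Week 16 assessments after early discontinuation, and chemistry is scheduled at both.
- FAS membership needs one dose and one post-dose value. Removed subjects therefore stay in the FAS, their earlier visits inform the MMRM, and Protocol 8.9.2 adds an LOCF ANCOVA.
- The PPS drops subjects altogether and also excludes some for AEs. A reader might infer that the FAS collapses into the PPS and that comparing them becomes pointless. The documents do not support that.
- SAP Section 3 says that summaries at or before a time point, with Week 12 ALP as its example, consider all assessments up to the end of the window. An early ALP might be used that way, but it would still be a carried-forward value, and the SAP does not tie this rule to the MMRM.
- A reader might infer that any unblinding under Protocol 6.5, where the "pharmacovigilance team may also be required to break the blind for regulatory reporting purposes", leads to removal. No passage says so. Section 5.4 speaks only of "due to any code-breaking requested by investigator/safety".
- The SAP 4.1 list is open-ended. The reason is also recorded on the eCRF and listed by subject, so losses can be traced.

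What remains is that the retention promise is best-effort, covers only the final visits, and does not fix the assessment at Day 84. Extrapolation from visits before removal, or LOCF, does not replace a measured Week 12 ALP.

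**Conclusion.** The point holds as a risk of avoidable missing data. Section 5.4 permits loss of follow-up on four grounds that need not end it, and the visit and window rules do not ensure a true Week 12 ALP for those subjects. Some deviators' Week 12 values may be missing from the FAS analysis, which would then contrast less with the PPS.

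The size cannot be derived, because the documents give only a 20% all-cause dropout rate. It would be tempting to read the 11% to 25% figures as expected bias. They follow directly from the assumed removal rates and the assumed absence of drug effect, and they take no account of earlier visits in the MMRM.

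Two limits apply. The available SAP describes itself as the interim analysis plan and does not define the PPS, so the FAS-versus-PPS argument rests on the protocol. The disposition categories are a minor alignment matter.

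**What to change.** - **Protocol 5.4:** state that non-compliance, protocol deviation, code-breaking, and non-permitted medication affecting only assessments or objectives do not by themselves end study follow-up. Record them as deviations. Keep consenting subjects on the scheduled visits with ALP through Day 84, whatever is decided elsewhere about study drug.
- **Leave unchanged:** the AE, pregnancy, eligibility-safety, medication-safety and investigator best-interest grounds.
- **Analysis text:** state that these ALP values enter the primary FAS MMRM, and add a sensitivity analysis that sets aside values after an ALP-altering drug.
- **SAP 4.1 (minor):** match the study-discontinuation reasons to 5.4 and drop the screen-failure category, which cannot apply to a randomized subject.

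The cost is wording and a few more blood draws that are already on the schedule. No extra subjects or procedures are needed. The downside is that the FAS estimate may be smaller and noisier, because it would include subjects who departed from the plan.

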5.5 SCHEDULE OF STUDY PROCEDURES

The Schedule of Study Procedures is shown in [Table 5.5-1](#). The visits should occur as close to the intended dates as possible. However, there is an acceptable \pm 3-day window for individual scheduled visits. Subjects attending any visits out of windows from Day 1 to Week 12/Early Withdrawal (EOT) Visit should be brought back into compliance with the overall study-visit schedule as soon as possible thereafter. Subjects will then return to the clinic at Week 16 (or 4 weeks after last dose) for an EOS follow-up visit.

Table 5.5-1 Schedule of Study Procedures

Study Procedure	Days -42 to -1 (Screening) ^a	Day 1	Wk 1	Wk 2	Wk 4	Wk 8	Wk 12 (EOT)/ Early Withdrawal	Wk 16 (EOS)/ Follow-up
Informed consent	X							
Demographics	X							
Medical history	X							
Inclusion/exclusion criteria	X	X						
Height	X							
Body weight	X	X			X	X	X	X
Physical exam	X	X		X	X	X	X	X
12-lead electrocardiogram	X	X					X	X
Vital signs	X	X	X	X	X	X	X	X
Colonoscopy ^b	X							
MRCP ^c	X							
Prior and concomitant medications	X	X	X	X	X	X	X	X
Randomization		X						
Study drug self-administration training		X	X	X	X			
Dispense study drug		X	X	X	X	X		
Study-drug compliance			X	X	X	X	X	
Adverse event evaluations		X	X	X	X	X	X	X
LISSA evaluations ^d		X	X	X	X	X	X	X
PK blood samples ^e		X	X	X	X	X	X	X
NRS Itch/Fatigue ^f		X	X		X		X	
5-D Pruritus		X	X	X	X	X	X	X
Mayo Partial IBD Score ^g	X	X	X	X	X	X	X	X
Chemistry	X	X	X	X	X	X	X	X
Hematology	X	X	X	X	X	X	X	X
Urinalysis	X	X			X		X	X
Lipid panel		X					X	
CA19-9 ^h	X							
p-ANCA	X							
ELF panel		X					X	

Table 5.5-1 Schedule of Study Procedures (cont'd)

Study Procedure	Days -42 to -1 (Screening)	Day 1	Wk 1	Wk 2	Wk 4	Wk 8	Wk 12 (EOT)/ Early Withdrawal	Wk 16 (EOS)/ Follow-up
Hepatitis and HIV screen	X							
Urine drug screen	X							
Pregnancy test ¹	X	X					X	X
C4 and serum bile acids		X					X	
Vitamin D		X					X	X
INR	X	X					X	X
[REDACTED]		[REDACTED]					[REDACTED]	
Anti-drug antibodies		X	X	X	X	X	X	X
Neutralizing antibodies		X	X	X	X	X	X	X
Exploratory biomarkers		X	X	X	X	X	X	X

C4 = 7-alpha-hydroxy-4-cholesten-3-one; CA19-9 = carbohydrate antigen 19-9; ELF = enhanced liver fibrosis; EOS = End of Study; EOT = End of Treatment; ERCP = endoscopic retrograde cholangiopancreatography; HIV = human immunodeficiency virus; IBD = inflammatory bowel disease; INR = International Normalized Ratio; LISSA = local injection-site symptom assessment; MRCP = magnetic resonance cholangiopancreatography; NRS = Numeric Rating Scale; p-ANCA = perinuclear anti-neutrophil cytoplasmic antibodies; PK = pharmacokinetic; Wk = week.

^a There must be a minimum of 14 days between Screening and Day 1 visits for adequate separation of the repeated Chemistry (liver function tests) and INR assessments.

^b Colonoscopy will be performed only in patients with concomitant IBD and who do not have a colonoscopy available within 12 months of Screening.

^c MRCP will be performed in all subjects at Screening.

^d LISSA evaluations will be performed pre-dose for all on-treatment visits.

^e PK blood samples will be collected before subjects dose themselves in the clinic (pre-dose). At Day 1 and Week 12, an additional PK blood sample will be collected 2 hours post-dose.

^f NRS Itch/Fatigue will be completed as a daily diary during Day 1 and Study Weeks 1, 4, and 12. Diary will be dispensed at the study visit prior to the collection week.

^g Mayo Partial IBD Score will be collected in all patients, independent of whether they have IBD or not.

^h A second CA19-9 sample may be collected during the Screening period a minimum of 4 weeks from the original Screening sample in order to meet Inclusion Criteria 3g.

ⁱ A serum pregnancy test will be performed on all female subjects at Screening, Week 12, and Week 16. A urine pregnancy test will be performed on all female subjects at Day 1 (pre-dose).

